## **List of abbreviations**

ADSUS = Adult Service Use Schedule

APQ = Alcohol Problems Questionnaire

AUQ = Alcohol Urge Questionnaire

ASSIST = Alcohol, Smoking and Substance Involvement Screening Test

BMQ = Beliefs About Medication Questionnaire

CIDI = Composite International Diagnostic Interview

CM = Contingency management

EQ-5D-5L – Health Related Quality of Life

MEMS = Medication Events Monitoring System

MM = Medication management

MMAS = Morisky Medication Adherence Scale

SADQ = Severity of Alcohol Dependence Questionnaire

SS = Standard support

STAR = Scale to Assess the Therapeutic Relationship

TLFB = Timeline Follow Back

## 1. Summary of research

Design: 3-arm, prospective, pragmatic, randomised controlled, parallel group clinical trial of strategies to enhance adherence to prescribed acamprosate for alcohol dependence. Standard support (SS), SS with adjunctive medication management (SS+MM), SS and MM with adjunctive contingency management (SS+MM+CM). Outcome assessment will be at 6 and 12 months post randomisation.

Setting: Specialist community alcohol treatment services, community pharmacies local to participants and a central telephone support service.

Population: Abstinent alcohol dependent adults, suitable for prescription of acamprosate, willing and able to provide informed consent.

Inclusion criteria: Aged  $\geq 18$ , ICD-10 alcohol dependence, currently abstinent from alcohol, commencing a prescription for acamprosate.

Exclusion criteria: Severe physical/mental illness identified by the treating clinicians, participation in another trial, unable to adequately understand verbal English, current dependence on an illicit substance.

Health technologies: MM provided by pharmacists via a central telephone support service (weekly for 6 weeks and then fortnightly for 6 weeks and then 4-weekly up to 24 weeks). MM plus CM: Small incentives (vouchers) will be provided to reinforce adherence to telephone support, ranging from £2 to £10 for each MM session completed, with a total value of up to £120 for completing all support sessions.

Primary outcome measure: Proportion of prescribed medication taken assessed using Medication Events Monitoring System (MEMS) and cross-verified using pill count and self-report at 6 months post randomisation.

Secondary outcomes: Proportion of prescribed medication taken, estimated by self-report at 12 months post-randomisation. Total alcohol consumed, drinks per drinking day, percent days abstinent in standard drinks (1 standard drink = 8g ethanol) in the previous 90 days derived using the Time Line Follow Back Form 90. Time to first drink, relapse to any drinking and relapse to heavy drinking (8+/6+ UK units for males/females on a single occasion) derived from self-report. Alcohol related problems (Alcohol Problems Questionnaire), alcohol craving (Alcohol Urge Questionnaire) and severity of alcohol dependence. Measured at baseline, 6 and 12 months post-randomisation.

Process outcome measures: Participants' beliefs about medications (BMQ; measured at baseline and 6 month follow-up), the therapeutic relationship with the care provider (STAR: measured at 6 month follow-up) adverse events (measured at each bi-monthly research visit).

Economic outcome measures: Health related quality of life (EQ-5D-5L) and Adult Service Use Schedule modified for alcohol-misusing populations measured at baseline, 6 and 12 months post-randomisation. Costs associated with the provision of control and trial interventions, including costs associated with delivery, training, management and overheads.

**Primary analysis:** The primary analysis will be conducted using an intention-to-treat approach. As the study involves three arms, the initial step of the primary analysis will use a multiple analysis of covariance, adjusted for stratification factors, to explore for overall effects between the three arms. If evidence of effect is observed a second analysis, using an analysis of covariance, will explore the mean differences in the primary outcome by comparing SS versus SS+MM and SS versus SS+MM+CM. All results will be presented with estimates of precision and associated 95% confidence intervals.

**Economic analysis:** Analysis of the costs and effects of MM with or without CM for alcohol dependence compared to SS. The primary economic perspective will be the health and social care provider perspective. Broader perspectives will be considered in sensitivity analyses (i.e. criminal justice contacts and criminal activity, patient and family costs).

**Sample size:** Differential allocation of the order of 2:1:1 to maximize the utility of resources with twice as many being allocated to the SS group than the intervention groups. A clinically important difference in adherence to medication is estimated as an effect size of the order of 0.3. To estimate this difference using power of 80%, alpha 0.05 with a 2 sided test requires 524 analysed at 6 months post-randomisation across the three groups. Allowing for attrition of 30%, less than observed in other trials in similar populations, requires a total sample size at allocation of 748; 374 allocated to SS, and 187 each to SS+MM and SS+MM+CM. In addition to addressing the primary outcome the sample size is sufficient to identify a clinically important difference effect size of 0.3 for alcohol consumption measures at both 6 and 12 months post randomization.

**Allocation:** Participants will be allocated following informed consent to take part and within one month of initiation of acamprosate. Allocation will be stratified by site, severity of alcohol dependence and the prescription of any other relapse prevention medication. As a pragmatic study interventionists will be unblinded with regard to participant allocation but follow-up assessments will be conducted blind.

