#### 7.1.1 Design and theoretical/conceptual framework

The study will be a 3-arm, pragmatic, randomised controlled, parallel group clinical trial. Each participant will be prescribed acamprosate as soon as possible after alcohol abstinence is achieved for a minimum duration of 24 weeks. Follow-up contacts with the research team will take place 6 (+30 days) and 12 (+60 days) months post randomisation. Participants will collect their medication monthly from the community pharmacy, which will be dispensed from designated pharmacies in bottles with MEMSCaps. Consented participants will be randomised (in the order of 2:1:1) to receive;

- SS consisting of monthly pick up of prescribed acamprosate from the community pharmacy and monthly follow-up with their specialist alcohol team for three months followed by monthly follow up with their GP for three months; or
- SS+ MM once a week for the first 6 weeks, reducing to once a fortnight for the following 6 weeks, and then monthly for 3 months, delivered by telephone by a trained pharmacist from a central telephone support service; or
- SS+MM+CM which will include incentivisation for completion of each of the telephone MM support sessions, with the pharmacist.

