#### *7.1.1.1 Treatment arm 1: Standard support (SS)*

All participants in the trial will be prescribed acamprosate (two 333mg tablets morning, afternoon and evening or two 333mg tablets in the morning and one 333mg tablet in the afternoon and evening if the service users body weight is below 60kg) as soon as possible following alcohol abstinence in addition to the psychosocial care normally provided. The decision to initiate acamprosate will be determined by the treating clinician in the specialist alcohol service in conjunction with the service user.

The NICE guideline on diagnosis, assessment and management of harmful drinking and alcohol dependence (13) recommends, "Service users taking acamprosate should stay under supervision, at least monthly, for 6 months, and at reduced but regular intervals if the drug is continued after 6 months" p426. In clinical practice, after completion of assisted alcohol withdrawal, service users remain under the care of the specialist alcohol service for up to three months before they are transferred back to the care of their GP for ongoing care including prescribing. The type, frequency and intensity of psychosocial intervention received vary between specialist alcohol services and between individual service users, dependent on their needs, local funding and services available. As this is a pragmatic RCT, SS will be the care normally provided by local participating services, and service use will be recorded for each participant. However, participating services have agreed to follow the NICE guideline with respect to acamprosate prescribing with trial participants. Based on the current service provision of the five proposed study centres, SS is monthly pick up of prescribed acamprosate from the community pharmacy and monthly monitoring of the service user for three months by the specialist alcohol service and then returned to the care of their GP for monthly monitoring in accordance with the NICE guidelines (13) and current NHS clinical practice. As the trial is pragmatic it will be possible for patients to continue being prescribed acamprosate beyond the 24 week period of medication adherence monitoring providing this is agreed between patients and clinicians, in accordance with NICE guidelines.

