#### 7.1.10 Data collection

Table 1 outlines the study outcome measures and timing of their administration during the study. Research and personal data will be collected using electronic data capture, specifically designed for this research study by Codeface Ltd, using a laptop computer. Laptop computers will be password protected. Data will be entered and saved on a secure server with a 256bit encryption, no data will be saved directly onto the laptop computer. Research data will be anonymised by assigning

each participant a unique ID number, personal data will be stored separately to the research data to maintain participant anonymity.

All of the study interventions will be audio recorded and a proportion will be reviewed by the research team to check the fidelity of the delivery of the intervention and inform further training. Audio files will be stored on a secure server with restricted access through password protected computers. Consent to take part in the research will be captured using an electronic consent form overseen by the researcher.

Table 1: Trial outcome measures, timing of administration and duration of participant completed questionnaires

		Baseline	Bi-Monthly visit (months 1 to 6)	6 month follow-up	12 month follow-up
CIDI	Diagnosis of alcohol dependence				
ASSIST	Psychoactive drug misuse				
SADQ	Severity of alcohol dependence				
AUQ	Current craving for alcohol				
APQ	Presence of alcohol related problems				
TLFB	Percentage of days abstinent and Units of alcohol per drinking day Time to first alcoholic drink Time to relapse to any drinking Time to relapse to heavy drinking.				

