BMQ	Beliefs about medication specific to their health and general medication beliefs				
EQ-5D-5L	Health related quality of life				
AD-SUS	Service use				
STAR	Therapeutic relationship with pharmacist delivering MM				
MMAS	Assess self-reported adherence to acamprosate				
MEMS	Percentage medication taken as prescribed				
Pill count	Percentage of pills taken				
Self-reported adherence	Percentage of pills taken Reasons for non-adherence				

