Alcohol related problems will be assessed at initial screening assessment and then at 6 and 12 month follow-up, using the Alcohol Problems Questionnaire (APQ; (4)). The APQ is a 46-item questionnaire assessing potential problems with psychological, physical, social, legal, employment, relationships and parenting that may be experienced due to alcohol. The Alcohol Urge Questionnaire (AUQ) (91) assesses current urge for alcohol using eight items which cover three factors: desire for a drink (4 items); expectation of positive effect from drinking (2 items); and inability to avoid drinking if alcohol was available (2 items). This questionnaire will be administered at initial screening assessment and at 6 and 12 month follow-up.

Health related quality of life will be measured using the EQ-5D-5L and participants' use of services will be measured using the Alcohol and Drug Adapted Adult Service Use Schedule (AD-SUS). These measures will be used to assess the cost-effectiveness of MM and MM+CM compared to SS. These measures will be collected at baseline assessment and at 6 and 12 month follow-up.

Participants will be asked at each bi-monthly research visit whether they have experienced any side effects from the medication. In addition, reasons for non-adherence will be recorded.

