## **10. Safety reporting**

A Serious Adverse Event (SAE) is defined as an untoward occurrence that;

- a. Results in death;
- b. Is life threatening
- c. Requires hospitalisation or prologation of an existing hospital stay;
- d. Results in persistent or significant disability or incapacity;
- e. Consists of a congenital anomaly or birth defect; or
- f. Is otherwise considered medically significant by the investigator.

The Chief Investigator will report an SAE to the Research Ethics Committee (REC) who provided favourable ethical opinion within 15 days of becoming aware of the event if the event is related (that is, resulted from administration of any of the research procedures), and unexpected (that is, the type of event is not listed in the protocol as an expected occurrence).

If an urgent safety measure is required, the Chief Investigator will immediately by telephone and then in writing within 3 days inform the REC who gave favourable ethical opinion the reasons for the urgent safety measures and the plan for further action.

The Chief Investigator will report on the safety of participants in annual progress report to the REC.

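### No scheduled, active adverse-event collection in months 7 to 12, although follow-up and possibly acamprosate continue; serious-event reporting in that period is passive

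*Protocol*

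**What the plan says.** **Where adverse events are collected.** Section 1 (process outcome measures) lists "adverse events (measured at each bi-monthly research visit". Section 7.1.10.2 describes the question itself: "Participants will be asked at each bi-monthly research visit whether they have experienced any side effects from the medication". The corresponding column of Table 1 in section 7.1.10 is headed "Bi-Monthly visit (months 1 to 6" and so ends at month 6. Table 1 has no adverse-event row.

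**How long participants are followed.** Section 7.1.1 states: "Follow-up contacts with the research team will take place 6 (+30 days) and 12 (+60 days) months post randomisation". Section 7.1.1.1 adds that "it will be possible for patients to continue being prescribed acamprosate beyond the 24 week period of medication adherence monitoring", if patient and clinician agree. Section 6 hypothesises better adherence and better cost-effectiveness at 12 months in the intervention arms, and section 7.2.5 sets the primary economic comparison at 12 months.

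**Safety reporting.** Section 10 defines SAEs and says: "The Chief Investigator will report an SAE to the Research Ethics Committee (REC) who provided favourable ethical opinion within 15 days of becoming aware". This applies to events that are both related and unexpected. It also says: "The Chief Investigator will report on the safety of participants in annual progress report to the REC". Neither duty has an end date.

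**Other 12-month data.** Table 1 ticks drinking (TLFB), dependence, craving, alcohol problems, service use (AD-SUS) and quality of life at 12 months. It also ticks a self-reported adherence row covering "Percentage of pills taken Reasons for non-adherence".

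**The concern.** Benefit and cost-effectiveness are to be claimed over 12 months, while harm is actively sought for about six. If medication management, with or without vouchers, raises adherence at 12 months as section 6 hypothesises, exposure to acamprosate would differ between arms in the very period with no scheduled harm question. A researcher following the protocol would see the participant at month 12 and ask about drinking, craving, service use and adherence, but would have no instruction to ask about adverse events.

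This is a matter of what is collected, so a later analysis plan cannot repair it. What is at stake is a like-for-like comparison of harms between arms in the second half of follow-up, and the completeness of what reaches the data monitoring committee and the ethics committee for that period.

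**Working it through.** The protocol gives no figure to reproduce. The check sets the adverse-event schedule against the follow-up schedule.

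**Inputs**
- Adverse-event question: bi-monthly visits only (sections 1 and 7.1.10.2).
- Bi-monthly visits: months 1 to 6 (Table 1).
- Prescribing and adherence-monitoring phase: 24 weeks (sections 7.1.1.1 and 7.1.10.1).
- Last contact: 12 months, window +60 days (section 7.1.1).
- Planned sample: 748 randomised, 524 analysed at 6 months (section 7.2.2).

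**Scheduled coverage** = months with a scheduled question ÷ months of follow-up
- 6 ÷ 12 = 50%.
- Counted by the 24-week phase: 24 ÷ 52 = 46%.

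**Length without a scheduled question** = last contact − last bi-monthly visit
- 12 − 6 = 6 months.
- With the full window, 60 days being about 2 months: 12 + 2 − 6 = about 8 months.

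**Planned follow-up time in months 7 to 12**
- 748 × 0.5 year = 374 person-years if everyone is followed.
- 524 × 0.5 year = 262 person-years if the number followed to 12 months equals the number analysed at 6 months (an assumption).

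These person-years cover all arms and count time in the study. They measure neither time on acamprosate nor extra exposure caused by the interventions. The protocol gives no adverse-event rate, so no count of missed events can be derived.

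**Does another provision fill the gap?**

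| Provision | Months 7–12? | Active harm question? |
|---|---|---|
| Bi-monthly side-effect question | No | Yes, while it runs |
| SAE reporting (section 10) | Yes, no end date | No; starts when the investigator becomes aware |
| AD-SUS at 12 months | Yes | No; service use, not linked to safety reporting |
| Reasons for non-adherence at 12 months | Yes | No; indirect, and not linked to safety reporting |
| TLFB at 12 months | Yes | Covers drinking and relapse only |

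No row supplies an active question about harms other than drinking after month 6.

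**Scope of the question itself.** Section 1 speaks of adverse events in general. Section 7.1.10.2 asks only about effects attributed to the medication. An admission that the participant does not attribute to acamprosate would meet the section 10 SAE definition, yet it is not clearly asked about even in months 1 to 6.

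**The case against.** The strongest defence is proportionality. The randomised interventions are telephone calls and vouchers that end at about 24 weeks. Acamprosate has been licensed in the UK since 1995 (section 5.1), is prescribed by the treating clinician in every arm, and remains under clinical monitoring. Side effects are a process measure tied to the adherence-monitoring phase, so ending active questioning with that phase is a defensible choice in a pragmatic trial. This stands as a limit on the weight of the point. It does not explain why an existing 12-month visit, used to compare adherence and cost-effectiveness between arms, should omit the question.

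A reader might also infer four stronger things that the protocol does not support:

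- **That half the follow-up has no adverse-event ascertainment at all.** Section 10 has no month-6 cut-off, and neither the ethics committee report nor the monitoring committee's review (section 4) is limited to the first six months. Ascertainment of serious events continues, though passively.
- **That relapse after the calls and vouchers stop goes unseen.** Table 1 ticks the TLFB at 12 months, with time to first drink and relapse among its outcomes, and section 7.2.4 plans survival analysis of relapse.
- **That the 6-month follow-up also lacks the question.** The bi-monthly column runs to month 6, so that visit may coincide with the 6-month follow-up. The secure gap is months 7 to 12.
- **That a given number of serious events would be missed.** The protocol gives no rate. Admissions may in any case appear in the AD-SUS, and section 5.3 reports side effects as a common reason for non-adherence in an earlier trial, so the 12-month adherence row could pick some up.

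These indirect routes are real, but nothing in the protocol directs the information they yield into safety reporting.

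**Conclusion.** The point holds as a gap in scheduled, active collection. After month 6 no adverse-event question is planned, which leaves about half of nominal follow-up uncovered: roughly six months, or up to about eight with the visit window. SAE reporting continues throughout but depends on someone bringing the event to the investigator's attention. The main loss is the between-arm comparison of harms other than relapse in months 7 to 12.

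This conclusion takes Table 1 and the two descriptions of the question at face value, and assumes that no other trial document adds an item at 12 months. It is an inexpensive improvement worth making. It does not show that participants are left without safety oversight, and it does not bear on the primary adherence analysis.

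**What to change.** 1. Add an adverse-event/SAE row to Table 1, ticked at the bi-monthly visits and at the 12-month contact, with the 12-month question covering the whole interval since the last visit.
2. State in section 10 that SAEs are collected up to the 12-month contact.
3. Cross-check recorded SAEs against the AD-SUS service-use data at 6 and 12 months, and state how an event found that way enters safety reporting.
4. Reconcile sections 1 and 7.1.10.2, so that it is clear whether all adverse events or only perceived side effects of the medication are asked about.

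With the added question, scheduled coverage rises from 6 of 12 months to 12 of 12, provided recall reaches back to the last bi-monthly visit. No extra visit is needed. The cost is a few minutes of interview time and a reconciliation of data already collected. The main weakness is recall of about six months at the last contact, which the AD-SUS cross-check partly offsets if the schedule records admissions.

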## **2. Trial Management Group**

The programme will be managed by a Trial Management Group (TMG) chaired by the Chief Investigator and will include all co-investigators and service user representatives. Collaborators will be included as required. The TMG will meet on a monthly basis throughout the course of the programme, either face to face or by teleconference.

## **3. Trial Steering Committee**

The TMG will report to an independent Trial Steering Committee (TSC) which will be convened on an annual basis as a minimum to approve the protocols and monitor the progress of the trial.

## **4. Data Monitoring and Ethics Committee**

An independent Data Monitoring and Ethics Committee will convene on an annual basis as a minimum to review the trial data and make recommendations to the TSC and TMG based on the ethical conduct and safety of the research.

## **5. Background and rationale**

Alcohol misuse is a global problem and is the third leading cause of disability in Europe (1). In the UK, there has been a consistent, year on year increase in harm related to alcohol. Alcohol-

related NHS hospital admissions have more than doubled since 2002/03, with an estimated 1,220,300 admissions related to alcohol in 2011/12 (2). Chronic health conditions related to alcohol have increased in prevalence in the UK, including liver cancer, pancreatitis, alcoholic liver-disease and alcohol use disorders (3). Mental health may be negatively affected by the chronic, heavy use of alcohol with increased risk of depression, anxiety, suicidality, psychosis and impairments to memory and other cognitive functions. Alcohol may contribute to social problems such as unemployment, criminality, marital breakdown, and domestic violence (4-7). The physical, mental and social problems associated with alcohol place a considerable burden on the UK economy. The estimated cost to the UK economy is £21 billion annually [18], of which the NHS costs are estimated at £3.5 billion (8).

The prevalence of alcohol dependence in the UK is estimated at 9.3% of men and 3.6% of women (9). The number of people entering specialist alcohol treatment has increased each year between 2008, when the Department of Health began collecting data, and 2012 (10). The number successfully completing treatment has also risen over the same reporting period but the majority of those dependent on alcohol undergo frequent episodes of withdrawal and resumption of drinking, as many as 70% of service users relapse in the first 12 months post treatment (11, 12). Improved treatment for alcohol dependence has been identified as a priority in the UK Government's Alcohol Strategy (8). Providing effective treatment for alcohol dependence to reduce relapse rates and therefore alcohol associated harms will contribute to this objective.

